#### **Deaths and Serious Adverse Events**

Summary tables and data displays will be provided for serious adverse events (as detailed in the study protocol). In addition, all deaths and serious AE's will be documented in a case narrative format in the clinical study report.

The number of deaths occurring over the treatment period will be summarized and Chi-squared test or Fisher's Exact test will be used to compare the number of deaths between treatment groups.

#### 1. Introduction

This statistical analysis plan (SAP) documents the planned statistical analyses for the TRACE-2 study and is based on the protocol, together with any subsequent amendments.

This SAP is intended for the use of project team members and should be read in conjunction with the aforementioned protocol.

#### 2. Study Objective

To evaluate the efficacy and safety of rhTNK-tPA (0.25 mg/kg) compared with standard rT-PA (0.9mg/kg) in the treatment of hyperacute ischemic stroke (within 4.5 h of symptom onset).

Primary study objectives:

To evaluate the difference in the proportion of 90-day mRS score of 0-1 between rhTNK-tPA (0.25 mg/kg) and standard rt-PA (0.9mg/kg) in the treatment of patients with hyperacute ischemic stroke (within 4.5 h of symptom onset).

Secondary study objectives:

- (1) To compare the difference in efficacy between rhTNK-tPA (0.25 mg/kg) and standard rt-PA (0.9mg/kg) in the treatment of hyperacute ischemic stroke (within 4.5 h of symptom onset):
  - 6) The proportion of patients with an mRS score of 0-2 at 90±7 days;
  - 7) MRS level distribution at 90±7 days (Shift Analysis /Ordinal Distribution);
  - 8) The proportion of patients whose NIHSS score is 0-1 or is improved compared to the baseline with  $\Delta$ NIHSS  $\geq$  4 at 24±2h, 7±1d or before discharge (whichever comes first);
  - 9) Health-related quality of life (EQ-5D) at 90±7 day;

- 10) The proportion of patients with a Bathel score  $\geq$  95 points at 90±7 days;
- (2) To compare the difference in safety between rhTNK-tPA (0.25 mg/kg) and standard rt-PA (0.9mg/kg) in the treatment of patients with hyperacute ischemic stroke (within 4.5 h of symptom onset):
  - 1) The incidence of symptomatic intracranial hemorrhage within 36 hours (as defined by ECASS III criteria);
  - 2) The incidence of symptomatic intracranial hemorrhage within 90 days (as defined by ECASS III criteria);
  - 3) The incidence of PH2 intracranial hemorrhage within 36 hours (according to SITS criteria);
  - 4) The incidence of any intracranial hemorrhage within 90 days;
  - 5) The incidence of other significant hemorrhage events within 90 days (as defined by GUSTO criteria);
  - 6) 90-day overall mortality;
  - 7) Incidence rates of adverse events/serious adverse events within 90 days.

#### 3. Study Endpoint(s)

Primary Efficacy Endpoints:

The proportion of patients with mRS score of 0-1 at 90 days.

Calculation formula:

The proportion of patients with 90-day mRS score of 0-1 = the number of patients with 90-day mRS score of 0-1 / the number of patients enrolled in this group  $\times 100\%$ .

#### Secondary Efficacy Endpoints:

- 6) The proportion of patients with an mRS score of 0-2 at 90±7 days;
- 7) MRS level distribution at 90±7 days (Shift Analysis /Ordinal Distribution);
- 8) The proportion of patients whose NIHSS score is 0-1 or is improved compared to the baseline with  $\Delta$ NIHSS  $\geq$  4 at 24±2h, 7±1d or before discharge (whichever comes first);
- 9) Health-related quality of life (EQ-5D) at 90±7 day;
- 10) the proportion of patients with a Bathel score ≥ 95 points at 90±7 days;

#### Safety Endpoint

- 8) The incidence of symptomatic intracranial hemorrhage within 36 hours (as defined by ECASS III criteria).
- 9) The incidence of symptomatic intracranial hemorrhage within 90 days (as defined by ECASS III criteria);
- 10) The incidence of PH2 intracranial hemorrhage within 36 hours (according to SITS criteria);
- 11) The incidence of any intracranial hemorrhage within 90 days;
- 12) The incidence of other significant hemorrhage events within 90 days (as defined by GUSTO criteria);
- 13) 90-day overall mortality;
- 14) Incidence rates of adverse events/serious adverse events within 90 days.

#### 4. Statistical Hypotheses

Comparison of the primary efficacy endpoint between groups is conducted by a one-sided test, with a significance level of one-sided  $\alpha$ =0.025. Null hypothesis H0: RR  $\leq \Delta$  and alternative hypothesis H1: RR  $> \Delta$ ; when P < 0.025, or lower limit of 95% CI of RR  $> \Delta$ , it indicates that the test drug is not inferior to control drug; RR is the ratio of incidence of the treatment group and the control group,  $\Delta$  is the non-inferior margin, 0.937 in this trial. All other statistical analyses are conducted by two-sided tests, with a significance level of two-sided  $\alpha$  =0.05. When P  $\leq$  0.05, it indicates a statistically significant difference. Non-inferiority hypothesis tests are as follows:

H0: 
$$RR$$
 Treatment group/control group  $\leq \Delta$   
H1:  $RR$  Treatment group/control group  $> \Delta$ 

#### 5. Design

This study will evaluate the efficacy and safety of rhTNK-tPA (0.25 mg/kg) compared with standard rt-PA (0.9mg/kg) in the treatment of hyperacute ischemic stroke (within 4.5 h of symptom onset). This is a multicenter, prospective, centrally randomized, open label, blinded-endpoint, parallel active controlled, non-inferior phase III clinical trial.

The drug administration method of the test drug (rhTNK-TPA) is as follows: according to the

body weight of the patients, the final dose is determined at 0.25mg/kg; Each vial is dissolved in 3ml of sterile water for injection to obtain a solution with a concentration of 5.33mg/ml. The amount required for medication is calculated and measured according to the actual body weight of the patient, 25mg at most. The solution is administered via single intravenous bolus injection in 5-10 seconds.

The administration method of active control drug (rt-PA) is as follows: The dose required for medication is calculated and measured according to the actual body weight of the patient based on a standard of 0.9 mg rt-PA/kg. The 10% of the dose is injected by intravenous bolus, and the remaining 90% is injected by intravenous drip within 1h.

The target population of this study is patients with critical hyperacute ischemic stroke (within 4.5 h of symptom onset), for whom considering the benefit of patients, intravenous thrombolytic therapy should be given as soon as possible after the onset, in order to achieve vascular recanalization or reperfusion and obtain a better prognosis. Due to the different administration methods of test drug and active control drug, and the inconvenience of the double-blind double-dummy design which may delay treatment and is not conducive to the benefit of patients. Therefore, this study adopts the form of open-label trial. To minimize bias, all endpoints will be evaluated in a blind manner by a qualified study physician.

#### Planned Analyses

The analyses that are detailed in this SAP will be performed only when the database has been locked, all protocol violators identified, and treatment allocations have been unblinded. Membership of the Full Analysis and Per Protocol populations will be determined using the rules set out in this SAP. The treatment allocations will be unblinded and extracted from corresponding system. These will then be merged on to the study database using the treatment number (as allocated to each patient) to match patients with the correct treatment allocation. Membership of the modified Intention-to-Treat and Per Protocol populations will be determined using the rules set out in this SAP and will be determined prior to unblinding the treatment allocation. At a date to be agreed within the project team, a data look will be performed. This will involve production of all data displays on a subset of the data using dummy treatment codes. These are produced purely as an aide to the pre-programming of the study and no unblinding will occur.

#### Interim Analyses

No interim analyses are planned for this study. However, a Data and Safety Monitoring Board (DSMB) is in place to ensure the safety of patients in the study. An independent statistician will prepare unblinded summary tables of SAEs, selected demographic data and exposure data and these will be examined by the DSMB. These tables will be provided to the DSMB at regular intervals. If the tables give rise to safety concerns for any treatment, the DSMB may recommend that the trial should be modified or stopped prematurely. The Steering Committee will, in conjunction with the Sponsor, decide whether to act on this recommendation. Further discussion of these safety tabulations is provided in a specific study protocol.

#### 6. Sample size estimates

In this study, rt-PA active control will be used based on a statistical hypothesis test of non-inferiority, and the proportion of patients with 90-day mRS score of 0-1 will be used as the primary efficacy endpoint.

According to a paper published in the Lancet [1] in 2014 about meta-analysis of the proportion of 90-day mRS score of 0-1 (treatment within 4.5h) regarding rt-PA versus Placebo, the RR and 95% confidence interval were 1.24 and 1.14-1.36, respectively. According to the *Guidelines for the Design of Non-inferiority Drug Clinical Trials* [2], the lower 95% confidence interval of the Meta analysis should be used to calculate the non-inferiority threshold given that the primary endpoint is a high priority index. Therefore, based on the lower CI limit of 1.14, together with an efficacy of 50% of the active control, the non-inferior threshold was determined as 0.937. Then assuming  $\alpha$ =0.025 using one-sided test, power 1- $\beta$ =0.85, treatment group (TNK) incidence of 63.64%, control group (rt-PA) incidence of 59.32%, RR= 1.07, the sample size was calculated to be 642 cases in each group; considering a dropout rate of 10%, the sample size was determined as 715 cases in each group and the total sample size is estimated to be 1430 cases.

#### 7. Analysis populations

According to National Medical Products Administration (NMPA), statistical analysis of data was established including Full Analysis Set (FAS), Per Protocol Set (PPS) and Safety Set (SS). The entire process of statistical analysis of data will be received strict control of quality in order to ensure facticity of data.

#### Full Analysis Set (FAS):

According to the basic principle of intention-to-treat (ITT), all patients who were enrolled, randomized and had the record of at least one-day treatment of study drugs will be included. This population was also referred as modified ITT population.

#### Per Protocol Set (PPS)

Per Protocol Set (PPS) is a subset of FAS. All patients with finishing the treatment without violating the trail program seriously or missing data for primary efficacy endpoints are included in PPS. The exact definition of a serious violation will be finalized at the time of data review and may generally include (but is not limited to) the following criteria: failure to meet the main inclusion

criteria, concomitant treatment that seriously interferes with the evaluation of the efficacy of study drugs after randomization, poor compliance, and exceed the time window of follow-up seriously and so on. A partial protocol violator will be included in the Per Protocol Population up to the time of their violation. For the Per Protocol Population, participants will be analyzed according to the treatment received, providing the same treatment was taken for the duration of the study. If study medication was changed then the participant will be considered a partial protocol violator (from the point of change onwards).

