#### 3.2 Grouping

The subjects are randomly divided 1:1 into two groups, the treatment group (rhTNK-tPA 0.25mg/kg) and the control group (rT-PA 0.9mg/kg), and are given treatment within 4.5h after symptom onset.

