#### 12. Statistical plan

## 12.1 Statistical analysis

Full analysis set (FAS), per protocol set (PPS) and safety analysis set (SAS) will be established according to the NMPA regulations for data statistical analysis. Strict quality control will be carried out in the whole process of data collection to ensure the authenticity of the evaluation data.

Full analysis set (FAS): a data set consisting of all subjects randomized to receive at least one study drug according to the basic principle of Intention To Treat.

Per protocol set (PPS): PPS includes all subjects who complete the stipulated treatment without missing primary efficacy endpoints or serious violations of the protocol. Serious protocol violation will be finally defined during data review and

may generally include (but not limited to) the following situations: subjects violating inclusion criteria or exclusion criteria, poor compliance in stipulated medication, concomitant medication that affects outcome indicators, and out of visit window.

Safety analysis set (SS): a set of all subjects participating in the trial, receiving at least one study drug, and having at least one safety evaluation.

FAS and PPS are established as sensitive analysis groups; Efficacy analysis is performed on the basis of FAS and PPS. Safety endpoints will be performed on the safety set and safety missing data will not be filled. All baseline demographic data analyses will be performed on the basis of the FAS; illogic data needs to be investigated by the data management facility, investigators or Sponsor together to identify possible reasons, and restrained by the parties in a data review meeting after full discussion: illogic data, if sufficient reasons have been found to indicate its incorrectness, should be removed, or otherwise, should be remained and subjected to analysis and the results obtained without such removed data should be treated as sensitivity analysis; If there is data collected in the study that is not in accordance with the program requirements such as planned external visits, it will be presented in a list, and descriptive or comparative analysis will be decided at the data review meeting depending on the specific situation of the data.

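### The final SAP groups the per-protocol set by drug received, which conflicts with the exclusion rules in the SAP and protocol and could count wrong-drug patients in the opposite arm

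*Supplement*

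**What the plan says.** Final SAP, section 7, Per Protocol Set: the PPS is a subset of the FAS, made up of patients who finish treatment without a serious violation and have primary endpoint data. The list of serious violations is open and is settled at data review. It names poor compliance but not receipt of the wrong study drug. The section then states that "participants will be analyzed according to the treatment received, providing the same treatment was taken for the duration of the study", and that a patient whose medication was changed becomes a partial violator from that point.

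Final SAP, section 11, Protocol Deviations: violators stay in the FAS and leave the PPS, with a distinction between full and partial violators.

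Final SAP, section 12: the primary efficacy analysis uses both FAS and PPS.

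Final SAP, section 7, Safety Set: patients treated in error are counted under the drug they actually received.

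Protocol V2.2, section 12.1: "PPS includes all subjects who complete the stipulated treatment without missing primary efficacy endpoints or serious violations of the protocol". Poor compliance with the stipulated medication is an example of a serious violation. The protocol contains no rule that assigns PPS patients by drug received.

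**The concern.** Protocol section 6.3 describes a single dose. A patient who was randomized to one drug and given only the other therefore always meets the proviso that the same treatment was taken throughout. For everyone who got the assigned drug, grouping by drug received and grouping by randomized arm are identical. The sentence can only affect wrong-drug patients, and what it does is place their outcomes in the opposite arm.

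Two things are at stake. First, the SAP gives two answers for the same patient, and the protocol's definition points to exclusion. Second, staff know the allocation before they treat (protocol section 3.4.1), so a switch of drug can be connected with how the patient looks. Excluding such a patient takes one outcome out of one arm. Moving the patient also adds that outcome to the other arm, in a set that carries the non-inferiority test.

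**Working it through.** **1. The plan's own figures.** Inputs from SAP section 6: alpha "0.025 using one-sided test"; power "0.85, treatment group (TNK) incidence of 63.64"% (that is, power 0.85); "treatment group (TNK) incidence of 63.64%, control group (rt-PA) incidence of 59.32%, RR= 1.07"; "the non-inferior threshold was determined as 0.937"; "considering a dropout rate of 10%, the sample size was determined as 715 cases in each group". Allocation is 1:1 (protocol section 3.2).

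- Margin: 1/√1.14 = 0.9366, in line with 0.937.
- Log risk ratio formula: n = [(1−p₁)/p₁ + (1−p₂)/p₂] × (1.960 + 1.036)² / [ln(1.07/0.937)]², with p₂ = 0.5932 and p₁ = 1.07 × 0.5932 = 0.6347. This gives 643 per arm. A linearised formula gives 641 and the Farrington-Manning formula gives 642. The stated figure is 642.
- Dropout: 642/0.9 rounds up to 714, against 715 stated.

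The sample size therefore reproduces, and the PPS sentence changes nothing in it.

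**2. The passages side by side, for a patient given only the other arm's drug.**

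| Text | What follows |
|---|---|
| SAP 7, treatment-received sentence | Kept, counted in the opposite arm |
| SAP 7, serious-violation test | Excluded if data review calls it serious; not named in the list |
| SAP 11, violators | Excluded, unless classed as a partial violator |
| Protocol 12.1 | Excluded: stipulated treatment not completed |
| SAP 7, Safety Set | Counted by actual drug, for safety only |

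If the exclusions always came first, the treatment-received sentence would have no work to do. The SAP does not say which rule has priority.

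**3. Illustration when the true risk ratio is 1.** These inputs are assumed: N = 643 evaluable per arm (642 gives the same results to three decimals), 60% success in both arms, and k wrong-drug patients in each arm. Patients randomized to tenecteplase but given alteplase succeed at 0.45; those switched the other way succeed at 0.75. N × p = 385.8.

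- Moved: RR = (Np − k·0.45 + k·0.75)/(Np − k·0.75 + k·0.45)
- Excluded: RR = (Np − k·0.45)/(Np − k·0.75)

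k = 14 (2% of 715): moved 390.0/381.6 = 1.022; excluded 379.5/375.3 = 1.011.

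k = 7 (1% of 715): moved 387.9/383.7 = 1.011; excluded 382.65/380.55 = 1.006.

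The distance from 1 to the margin is 1 − 0.937 = 0.063. With k = 14 the rule adds 1.022 − 1.011 = 0.011 over exclusion, and 0.011/0.063 is about 17%. If the prognosis gap is reversed, the moved result is 381.6/390.0 = 0.978. With no gap it is 1.000.

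**4. Illustration at the margin.** True RR 0.937, control rate 0.5932, 642 per arm. Correctly treated patients keep these rates, so exclusion gives RR 0.937 and one-sided alpha 0.025 by construction. Wrong-drug patients are assumed to succeed at 0.7 or 0.5 times the rate for the drug received.

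| Wrong-drug patients (assumed) | RR if moved (0.7 / 0.5) | One-sided alpha (0.7 / 0.5) |
|---|---|---|
| 1%, tenecteplase arm given alteplase | 0.940 / 0.942 | 0.029 / 0.032 |
| 2%, same direction | 0.943 / 0.946 | 0.033 / 0.040 |
| 5%, same direction | 0.951 / 0.960 | 0.048 / 0.072 |
| 2%, opposite direction | 0.932 / 0.928 | 0.019 / 0.015 |
| 0.5% to 5%, equal in both arms | 0.937 | 0.025 |

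With average prognosis there is no shift in any row.

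**The case against.** The strongest reply is that the SAP already excludes these patients. Receipt of the wrong drug is plainly a serious violation, section 11 removes violators, and protocol section 4.4 removes cases that did not take the stipulated medication where efficacy can then not be judged. On that reading everyone left in the PPS received the assigned drug and the sentence is idle. This reading is available, so the documents do not establish that a wrong-drug patient is certain to be kept and moved. They also do not rule it out: the wrong drug is not named as a serious violation and no order of rules is given. The need to reconcile the texts remains.

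A reader might infer that the sentence turns the PPS analysis into a non-randomized as-treated comparison. The documents do not support that. Only wrong-drug patients could change arm. Any PPS is already a selection made after randomization, and excluding these patients would not restore randomization either.

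A reader might also take the whole shift to 1.022, about a third of 0.063, as the damage done by the rule. Half of that shift remains after exclusion, so the rule itself accounts for about a sixth. The doubling relative to exclusion belongs to that constructed case and is not general.

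Two safeguards also count. The FAS follows the intention-to-treat principle and is analysed beside the PPS. Drug labels carry the subject's random number, and subject number and dosage are checked before dosing (protocol sections 5.2 and 6.3), so wrong-drug patients may be few.

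**Conclusion.** The point stands as a conflict between rules for one of the two sets used in the primary analysis. The treatment-received sentence acts only on patients given the other arm's drug, would place them in the opposite arm, and runs against SAP section 11 and protocol section 12.1.

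Its numerical effect is unknown because no rate of wrong-drug treatment is given. It is zero if such patients are prognostically average. In the section 4 model above it is also zero if errors are equal in both arms with the same prognosis. Otherwise it can favour either drug. Under the assumed 2% per arm with a 30-point gap, the rule adds about 0.011 to the risk ratio over exclusion. Under assumed one-directional errors of 1% to 2% with poor prognosis, one-sided alpha at the margin rises from 0.025 to between 0.029 and 0.040. These are illustrations of what could happen, not estimates for this trial. The correction is worth making because the text is contradictory and the remedy is nearly free.

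**What to change.** In final SAP section 7, replace the treatment-received sentence with:

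> *Receipt of the non-assigned study drug is a serious protocol violation and excludes the patient from the PPS; FAS and PPS are analysed by randomized arm, and grouping by drug received is used only in the Safety Set.*

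This brings section 7 into line with SAP section 11 and protocol section 12.1. It changes no planned sample size, alpha or power. The cost is one sentence, and the PPS may lose a few patients.

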#### Safety Set (SS)

All patients who received at least 1-time of study drug according to the study protocol and safety assessment available will be included in the safety population. Throughout the safety results sections, erroneously treated patients (eg, those randomized to rhTNK-tPA group but actually given rhTNK-tPA) will be accounted for in the actual treatment group. This population will be used for safety analyses.

#### 8. Treatment comparisons

The treatment comparison of interest in this study is to evaluate the efficacy and safety of rhTNK-tPA (0.25 mg/kg) versus standard rt-PA (0.9mg/kg) in Chinese patients in the treatment of hyperacute ischemic stroke (within 4.5 h of symptom onset).

#### 9. General considerations for data analyses

All programming will be performed using SAS Version 9.4 or superior. The content of statistical analysis is the general principle of statistical analysis method, and the detail process will refer to protocol. All analysis output will use the following treatment group naming conventions and treatment order:

Treatment group(rhTNK-TPA): RhTNK-TPA 0.25mg/kg: Each vial is dissolved in 3ml of sterile water for injection to obtain a solution with a concentration of 5.33mg/ml. The amount required for medication is calculated and measured according to the actual body weight of the patient, 25mg at most. The solution is administered via single intravenous bolus injection in 5-10 seconds.

Control group(rt-PA): rt-PA 0.9mg/kg: The product is dissolved in sterile water for injection to obtain a solution with a concentration of 1mg/ ml. The amount required for medication is calculated and measured according to the actual body weight of the patient. The 10% of the solution is injected by intravenous bolus, and the remaining 90% is injected by intravenous drip

within 1h.

